3.2.4 Pharmacokinetics

In Study BGJ398X2101, full PK profiles were obtained on Day 1, Day 15 and Day 28 after the first dose of study drug. As this study is ongoing, all data presented are current as of 24 September 2013 (refer to the Investigator Brochure for further details).

At 5 and 10 mg/day, plasma concentrations of BGJ398 were low (< 3.3 ng/mL) and frequently below the lower limit of quantification. Exposure (C_{max} and AUC) was measurable in all treated patients starting at 20 mg/day.

The median apparent T_{max} value across all dose levels tended to be 2-3 hours post-dose. At the MTD (125 mg q.d.), the median C_{max} and AUC₀₋₂₄ were ~80.8 ng/ml and ~694 h.ng/ml on Day 1 and ~245 ng/mL and ~3342 h.ng/mL on Day 15. At 125 mg q.d. 3 weeks on 1 week off, median C_{max} and AUC₀₋₂₄ were ~71.3 ng/mL and ~632 h.ng/mL on Day 1 and 251 ng/mL and 3693 h.ng/mL on Day 15.

The inter-patient variability was moderate to high for BGJ398 and % coefficient of variation (% CV) ranged from 50 – 75% at the expansion cohort of 125 mg qd on Day 15. Accumulation was observed with daily dosing. The mean AUC₀₋₂₄ ratios between Cycle 1 Day 1 and Cycle 1 Day 15 ranged from 1.5 to 6.5, which indicates some change in BGJ398 exposure following multiple dosing. At doses of 60 mg and above, most individual patients showed increased exposure on Day 15 following multiple dosing (~1.5 – 13 fold relative to Day 1 exposure). Very limited data are available for patients who received continuous dosing for 28 days without dose interruptions (8 patients at doses 60 mg and above, only 7 patients with PK data). In most of these patients who received uninterrupted dosing, a further increase in exposure beyond Day 15 was observed. This is based on either AUC₀₋₂₄ exposure on Day 28 or comparing predose samples after Day 15 in these patients. Refer to the BGJ398 Investigator's Brochure for further details.

MEMORIAL SLOAN-KETTERING CANCER CENTER IRB PROTOCOL

IRB#: 14-140 A (7)

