5.2.3 Administration of BGJ398

BGJ398 will be taken orally, using treatment schedule A (once a day for 21 days on, 7 days off) or treatment schedule B (once daily for 7 days on, 21 days off) repeating in 28 day cycles. Patients should be instructed to take the daily dose of BGJ398 in the morning, at approximately the same time each day (24 ± 2 hour interval). Patients should consume a light breakfast each day (e.g., non-grapefruit-based juice, toast and jam). This should be followed by a 2 hour fast, after which the doses of study drug should be taken. Patients should continue to fast for 1 hour after the administration of study drug.

BGJ398 should be taken with a large glass of water (~250 mL) and consumed over as short a time as possible. Patients should be instructed to swallow the capsules whole and not chew them. If for any reason a breakfast was not consumed prior to taking the dose the patient should take the dose with a full glass of water, and continue to fast for an hour after taking the dose. If the patient forgets to take the scheduled dose in the morning, he/she should not take the dose more than 2 hours after the usual time and should continue treatment the next day. Any doses that are missed should be skipped altogether and should not be replaced or made up at the next scheduled dosing.

If vomiting occurs following the dosing of study drug, re-dosing is not permitted that same day. Dosing should resume the next day. BGJ398 is characterized by pH-dependent solubility, and therefore, medicinal products that alter the pH of the upper gastro-intestinal tract may alter the solubility of both compounds, and limit bioavailability. These agents include, but are not limited to, proton-pump inhibitors (e.g., omeprazole), H₂-antagonists (e.g., ranitidine) and antacids. Therefore, BGJ398 should be dosed at least 2 hours before or 10 hours after dosing with a gastric protection agent. Patients must avoid consuming Seville oranges or juice, grapefruit, grapefruit juice, grapefruit hybrids, or pummelos from 7 days prior to the first dose of study medication through the end of study participation. This is due to a potential CYP3A4 interaction with study medication. Normal oranges and orange juice are allowed.

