9.0 TREATMENT/INTERVENTION PLAN

Treatment will be administered on an outpatient basis. Reported adverse events and potential risks are described in Section 11. Appropriate dose modifications of imatinib and BGJ398 are described in section 9.2. No investigational or commercial agents or therapies other than those described below may be administered with the intent to treat the patient's malignancy.

MEMORIAL SLOAN-KETTERING CANCER CENTER IRB PROTOCOL

IRB#: 14-140 A (7)

Imatinib will be self administered orally by the patient on a daily basis throughout the treatment cycle. The standard treatment dose is 400 mg PO QD. 400 mg capsule will be used unless otherwise specified by the treating physician. BGJ398 will be taken at the RP2D and treatment schedule chosen from the Phase Ib portion of the trial. The RP2D selected may be lower than the MTD based on PK data and clinical tolerance beyond Cycle 1. BGJ398 is taken daily for a duration determined by the treatment schedule appropriate for the given dose level. In the event of dose delays of BGJ398, Day 1 of the following cycle will be defined as the day that BGJ398 is restarted. A pill diary for both medications will be provided and recorded (Appendix B). This will be used to assure compliance with the regimen.

On the Phase Ib portion, the timing of pharmacokinetic sample collections will be dependent on the treatment schedule onto which that patient is enrolled. For treatment schedule A pharmacokinetic samples will be drawn on Cycle 1, Day 1 at the following timepoints: 0, 1, 2, 4, 6, 8, and 24 hrs; and Cycle 1, Day 21 at the following timepoints: 0, 1, 2, 4, 6, and 8 hours. For treatment schedule B pharmacokinetic samples will be drawn on Cycle 1, Day 1 at the following timepoints: 0, 1, 2, 4, 6, 8, and 24 hrs; Cycle 1, Day 7 at the following timepoints: : 0, 1, 2, 4, 6, and 8 hours, Cycle 1, Day 15 at timepoint 0hr and Cycle 1, Day 21 at timepoint 0hr.

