Using treatment schedule A, if dose level 1 to -2 is identified as the MTD and concern exists regarding therapeutic activity of BGJ398 at this dose level, expansions with higher dose levels (1 to 3) may be considered at the MSKCC PI's discretion, with modification of the treatment schedule. In this setting BGJ398 will be administered daily for one week followed by 3 weeks off and imatinib will be taken

**MEMORIAL SLOAN-KETTERING CANCER CENTER
IRB PROTOCOL**

IRB#: 14-140 A (7)

daily throughout the 4 week cycle period (treatment schedule B). The higher dose level expansion will start by enrolling 3 patients into a cohort, at dose level 1, using treatment schedule B.

When using treatment schedule B the maximum pace of dose escalation within each cohort is outlined in Table2.

Upon documentation of the RP2D dose and treatment schedule of the combination, the phase II trial will open and all subsequent patients enrolled will initiate treatment at that dose and treatment schedule with any subsequent dose modifications as outlined below.

Toxicity will be assessed using the NCI CTCAE (version 4.03) unless otherwise specified. Dose Limiting Toxicity (DLT) is defined as an unexpected adverse event (AE) or abnormal laboratory value assessed as at least possibly related to the study medication, which occurs ≤ 28 days (1 cycle) following the first dose of BGJ398 (cycle 1), and meets any of the criteria listed in Table 3. Please note plasma assessments may substitute for serum assessments per local laboratory standards.

Table 3: Criteria for defining dose-limiting toxicities

TOXICITY	DLT CRITERIA
Hematology	CTCAE grade 4 neutropenia lasting more than 7 consecutive days
	CTCAE grade 4 thrombocytopenia
	CTCAE Grade 3 or 4 neutropenia with fever (temperature $\geq 38.5^{\circ}\text{C}$)
Skin and subcutaneous tissue disorders	Rash, HFSR (Hand Foot Skin Reaction) or photosensitivity CTCAE Grade 3 > 7 consecutive days despite skin toxicity treatment (as per local practice)
	Rash, HFSR or photosensitivity CTCAE Grade 4
Eye disorders	CSR (Central Serous Retinopathy) CTCAE Grade 2 for > 14 consecutive days confirmed by ophthalmologic examination
	CSR (Central Serous Retinopathy) CTCAE Grade ≥ 3 , confirmed by ophthalmologic examination
	Retinal disorder other than CSR (retinal detachment/tear, retinal vascular disorder, retinopathy other) CTCAE Grade ≥ 2 confirmed by ophthalmologic examination

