	Visual disturbances without ocular (retinal) changes: Blurred vision, Flashing lights, Floaters, Corneal abnormalities CTCAE Grade ≥ 3
Gastro-intestinal	\geq CTCAE grade 3 nausea or vomiting ≥ 48 hrs despite optimal anti-emetic therapy
	\geq CTCAE grade 3 diarrhea ≥ 48 hrs despite optimal anti-diarrhea treatment
	Pancreatitis \geq CTCAE grade 3
Hepato-biliary	\geq CTCAE grade 3 total bilirubin
	\geq CTCAE grade 3 ALT (isolated increases in AST without concomitant increases

**MEMORIAL SLOAN-KETTERING CANCER CENTER
IRB PROTOCOL**

IRB#: 14-140 A (7)

	in ALT will not be considered dose-limiting, because of the non-specific nature of AST)
	Serum alkaline phosphatase CTCAE Grade 4 > 7 consecutive days
Investigations (Metabolic)	Serum Lipase and/or serum amylase (asymptomatic) CTCAE grade 3 for > 7 consecutive days Serum Lipase and/or serum amylase (asymptomatic) CTCAE grade 4 Symptomatic serum lipase and/or serum amylase ≥ CTCAE grade 3
ECG QT Interval	QTcF interval ≥ 501 ms on at least two separate ECGs
Renal	Serum creatinine > 2x ULN Serum Phosphorous that requires dose interruption of BGJ398 for >14 days of first 21 days of Cycle 1
Non-hematologic events	≥ CTCAE grade 3, except for the exclusions noted below
Exceptions to DLT criteria	Grade 3 alopecia
	< 5 days of CTCAE grade 3 fatigue
	< 5 days of CTCAE grade 3 edema
	Grade 3 laboratory abnormalities that are responsive to oral supplementation or deemed by the investigator to be clinically insignificant
CTCAE version 4.03 will be used for all grading. Optimal therapy for vomiting or diarrhea will be based in institutional guidelines, with consideration of the prohibited medications listed in this protocol.	

Phase II: The RP2D doses and treatment schedule defined in the phase Ib clinical trial will be used to conduct the phase II portion of the study.

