12.1.1 Definitions

Evaluable for toxicity. All Phase Ib patients will be evaluable for toxicity from the time of their first treatment with imatinib plus BGJ398. All Phase II patients will be evaluable for toxicity from the time of their first treatment with imatinib alone.

Evaluable for efficacy. Only those patients who have measurable disease present at baseline and have received at least one dose of imatinib plus BGJ398 therapy will be considered evaluable for efficacy. These patients will have their response classified according to the definitions stated below. Patients on the Phase II portion who are taken off study prior to receiving their first dose of BGJ398 for reasons other than progressive disease are considered replaceable for the purposes of evaluating primary and secondary endpoints.

Evaluable Non-Target Disease Response. Patients who have lesions present at baseline that are evaluable but do not meet the definitions of measurable disease, have received at least one cycle of therapy, and have had their disease re-evaluated will be considered evaluable for non-target disease. The response assessment is based on the presence, absence, or unequivocal progression of the lesions.

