The secondary endpoints of the phase 1b portion are (1) Response Rate (RR) defined by RECIST 1.1 criteria and by CHOI criteria, (2) Progression Free Survival (PFS), (3) Clinical Benefit Rate (CBR) at 32 weeks, and (4) BGJ398 pharmacokinetic parameters, such as area under the curve (AUC) and maximum concentration (C_{max}). RR will be estimated as the proportion of patients who have complete response or partial response for each criterion. PFS will be calculated using Kaplan-Meier estimate among all patients enrolled at each dose level. Patients who have not experienced the event of interest by the end of the study will be censored at the time of the last follow-up. Plasma concentrations of BGJ398 will be analyzed at multiple time points and expressed as a mean +/- SE.

The phase 1b portion of the study will have a minimum sample size of 6 patients and a maximum of 30. We expect to accrue approximately 2 patients each month, and hence expect to finish the phase 1b portion of the study in approximately 9-15 months.

Evaluable patients for safety analysis include all patients who have received one dose of imatinib plus BGJ398. Patients who stop therapy before Cycle 2, Day 1 for reasons other than toxicity will be replaced in the Phase I study for the purposes of evaluating the DLT. Evaluable patients for efficacy include all patients who have received one dose of imatinib plus BGJ398. Patients who are missing an assessment of response post baseline will be considered non-responders for that time point.

Patients on the Phase I portion of the study will not be included in the final efficacy analysis due to differences in the eligibility criteria in the two phases.

Phase 2 Portion Study Design and Endpoint Assessment

The primary endpoint of the phase II portion of the study is to assess Response Rate (CR+PR, RECIST 1.1) after 32 weeks of combination therapy. In order to detect a 20% improvement in the RR over imatinib alone (unacceptable rate of 45%; acceptable rate of 65%), 44 Phase II patients will be enrolled. At the end of the study, if > 24 patients have had a documented response by RECIST 1.1, the study will be considered positive and the treatment regimen will be considered worthy of further investigation. The study design is based on an exact Binomial test and has a one-sided type I error of 0.08 and a type II error of 0.1.

We expect to accrue 2 patients each month, and hence expect to finish the phase 2 portion of the study in 24 months.

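### The phase Ib DLT replacement rule sets no minimum cycle-1 BGJ398 exposure, so an under-dosed patient who stays on study counts as DLT-free in Table 2

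*Combined protocol and SAP*

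**What the plan says.** The evaluability text in Section 14.0 (phase Ib portion) begins with the safety set: "Evaluable patients for safety analysis include all patients who have received one dose of imatinib plus BGJ398". Section 12.1.1 is in line with this: "All Phase Ib patients will be evaluable for toxicity from the time of their first treatment with imatinib plus BGJ398". Replacement for DLT purposes is governed by the next sentence of Section 14.0: "Patients who stop therapy before Cycle 2, Day 1 for reasons other than toxicity will be replaced in the Phase I study".

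The DLT definition in Section 9.1 covers an event "which occurs ≤ 28 days (1 cycle) following the first dose of BGJ398 (cycle 1), and meets any of the criteria listed in Table 3". Table 2 then counts patients with a DLT out of three or six, without saying who qualifies for that denominator. No section asks for a minimum number or share of cycle-1 BGJ398 doses.

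Doses can be lost without the patient leaving treatment. Section 5.2.3 states: "Any doses that are missed should be skipped altogether and should not be replaced or made up at the next scheduled dosing". Section 13.0 allows local procedures, with all study drugs held around them and then resumed, and does not exclude cycle 1.

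Three rules limit the problem:
- Table 3 makes one kind of interruption a DLT: "Serum Phosphorous that requires dose interruption of BGJ398 for >14 days of first 21 days of Cycle 1".
- Section 9.3.2 says a BGJ398 delay of more than 14 consecutive days should end study treatment, but lets the lead-site principal investigator agree to continuation. The note closing Table 7 says that after a delay of more than 14 days treatment must stop, and gives no exception.
- Section 13.0 removes patients who cannot comply with treatment or evaluation, or whose intercurrent illness prevents further treatment.

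**The concern.** Finding the MTD is the primary endpoint of phase Ib, and each 3+3 decision rests on three or six patients. A patient who reaches Cycle 2 Day 1 after missing much of the planned BGJ398 for reasons unrelated to the drug has not stopped therapy. That patient is not replaced and is counted as having tolerated the dose. The resulting bias always runs towards calling the level safe, and the outcome feeds the phase II dose.

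Exposure matters for this drug because plasma levels build up. Section 3.2.4 reports: "Accumulation was observed with daily dosing". A short or broken course may therefore never reach the exposure that the level is meant to test.

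**Working it through.** **The plan's own figure.** Table 1 has five dose levels. At six patients each, 5 × 6 = 30, which matches the stated phase Ib maximum; 30 patients at 2 per month is 15 months, the stated upper bound. No planned figure is disputed.

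**How much exposure can be lost.** On Schedule A, 21 doses are planned. Suppose a patient takes Days 1 to 3, is held on Days 4 to 17 for a non-toxicity reason, and resumes on Days 18 to 21. That is 3 + 4 = 7 doses, and 7/21 = 33%. The hold is 14 days, so the rule for delays of more than 14 days is not met. The cause is not phosphate, so Table 3 is not met. Therapy was not stopped, so the replacement rule is not met. On Schedule B only 7 doses are planned, and three missed doses remove 3/7 = 43%.

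**Effect on escalation under Table 2.** Inputs:
- The rule: escalate on 0/3, or on 1/3 followed by 0 of the next 3.
- p, the true DLT risk at full exposure: assumed 30% or 40%.
- One under-exposed patient in every three: assumed.
- r, the share of the DLT risk that this patient keeps: assumed 0 or 1/3.

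The documents give none of p, the frequency or r.

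For a group of three, let a0 and a1 be the probabilities of no DLT and of exactly one DLT. Then P(escalate) = a0 + a1 × a0.
- All fully exposed: a0 = (1−p)³ and a1 = 3p(1−p)².
- One under-exposed: a0 = (1−p)²(1−rp) and a1 = 2p(1−p)(1−rp) + (1−p)²rp.

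At p = 30%:
- All exposed: 0.343 + 0.441 × 0.343 = 0.494.
- One in three, r = 1/3: 0.441 + 0.427 × 0.441 = 0.629.
- One in three, r = 0: 0.490 + 0.420 × 0.490 = 0.696.

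At p = 40%:
- All exposed: 0.216 + 0.432 × 0.216 = 0.309.
- One in three, r = 1/3: 0.312 + 0.464 × 0.312 = 0.457.
- One in three, r = 0: 0.360 + 0.480 × 0.360 = 0.533.

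If only the first group of three contains such a patient and r = 0, the results are 0.490 + 0.420 × 0.343 = 0.634 at 30% and 0.360 + 0.480 × 0.216 = 0.464 at 40%.

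**The case against.** The strongest reply is that existing rules already catch the worst cases. Removal for inability to comply or for intercurrent illness is a non-toxicity stop, so Section 14.0 would replace that patient. Long delays lead to stopping, and long phosphate interruptions are DLTs. Significant past non-adherence is an exclusion, missed doses are recorded, and cycle 1 has weekly examinations. This stands as a limit on the size of the problem. What remains is scattered missed doses and holds of up to 14 days. The phosphate rule covers one cause, the Section 9.3.2 delay rule covers consecutive days and can be waived, and removal for non-compliance has no stated dose threshold.

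Four stronger readings are tempting, and the documents do not support them.
- A reader might infer that the one-dose sentence is itself the fault. It defines the safety set, where one dose is normal; the replacement sentence is the operative one.
- A reader might infer that escalation can rest on patients barely exposed. Under the delay rule alone, doses on Days 1 and 16 only (2 of 21, with gaps of 14 and 12 days before Day 29) would pass, but removal for non-compliance would plausibly reach such a patient.
- A reader might take the rise in median AUC from about 632 h·ng/mL on Day 1 to 3693 on Day 15 (5.8-fold) as the size of the exposure deficit. Those figures are for 125 mg monotherapy. This trial starts at 75 mg, Section 3.2.4 gives mean ratios from 1.5 to 6.5, and Day 15 does not describe Schedule B, where dosing ends on Day 7.
- A reader might infer that the RP2D would simply be set wrongly. At least six patients are required at that dose, a lower one may be chosen on PK and later tolerance, and BGJ398 is sampled on Day 1 and again on Day 21 (Schedule A) or Day 7 (Schedule B), so under-exposure would often be visible. That review is discretionary, however, and does not change how Table 2 counts a patient.

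Vomited doses also cannot be assumed to be a non-toxicity loss, since vomiting may be treatment-related and has its own DLT criterion.

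**Conclusion.** The concern holds in a limited form. The plan has no minimum cycle-1 BGJ398 exposure for a DLT-free patient to count, and its partial safeguards leave intermittent missed doses and non-toxicity holds of up to 14 days uncovered. If one patient in every three is affected, the probability of escalating past a dose rises by 0.14 to 0.20 at a true DLT rate of 30%, and by 0.15 to 0.22 at 40%. These sizes depend on an assumed frequency and an assumed residual risk. Heavy non-toxicity dose loss in cycle 1 may be uncommon, in which case the effect is smaller. This is a cheap improvement to the escalation rule, not evidence that the phase Ib design is unsound.

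**What to change.** In Section 14.0, next to the replacement sentence, define a patient as DLT-evaluable for Table 2 if he or she:
- (a) had a DLT; or
- (b) completed the 28-day window and took at least a pre-specified share of planned cycle-1 BGJ398 doses, by diary and capsule count. As an example, 75% gives 0.75 × 21 = 15.75, so 16 of 21 on Schedule A, and 0.75 × 7 = 5.25, so 6 of 7 on Schedule B. The sponsor sets the figure; or
- (c) fell short of (b) because doses were missed, held or stopped for drug-related toxicity, including treatment-related vomiting. These patients stay in the denominator, are not replaced, and are listed separately with their exposure at the escalation decision.

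Replace patients who fall short of (b) for any other reason. Category (c) is needed because phosphate-driven holds that are not DLTs are foreseeable; without it such patients would be neither evaluable nor replaced, and the three or six in Table 2 could not be filled. Keep the one-dose definition for the safety set. Separately, reconcile the Section 9.3.2 text with the note closing Table 7 on delays beyond 14 days.

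The cost is a short definition, since diaries and capsule counts are already collected, plus an occasional replacement patient and a short cohort delay.
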